## 6.6 CONTINUED ACCESS TO INTERVENTION AFTER THE END OF THE STUDY

After normal completion of the IMP, patient will not receive additional doses.

## 6.7 TREATMENT OF OVERDOSE

In the event of an overdose, the Investigator should:

1. Contact the Sponsor or Sponsor representatives immediately.
2. Closely monitor the participant for any AE/SAE and laboratory abnormalities until recovery to Grade  $\leq$ 1
3. Document appropriately in the CRF.

Decisions regarding dose interruptions or modifications will be made by the Investigator in consultation with the Sponsor or Sponsor representatives based on the clinical evaluation of the participant.

## 6.8 CONCOMITANT THERAPY

Any medication or vaccine (including over the counter or prescription medicines, vitamins, and/or herbal supplements) or other specific categories of interest) that the participant is receiving at the time of enrollment or receives during the study must be recorded along with:

- Reason for use
- Dates of administration including start and end dates

The Sponsor or Sponsor representatives should be contacted if there are any questions regarding concomitant or prior therapy. The following therapies/medications are prohibited throughout the active treatment phase in relation to amcnestrant and/or tamoxifen treatment:

- Any concurrent anti-cancer treatment (surgery, radiotherapy, systemic therapy) except for participants diagnosed during the study with a second primary malignancy not requiring systemic therapy (ie, chemotherapy, hormonal therapy, targeted therapy, etc) and for whom study treatment is temporarily suspended to allow local treatment (surgery and/or radiation).
- Drugs that are strong inducers of CYP3A (including St John's Wort and genistein used as herbal medicine or food supplement, rifampin, avasimibe, rifapentine, phenytoin, carbamazepine, lumacaftor, phenobarbital) since they may decrease amcnestrant exposure.
- Drugs that are sensitive substrates of OATP1B1/1B3 including asunaprevir, atorvastatin, bosentan, danoprevir, fexofenadine, glyburide, nateglinide, pitavastatin, pravastatin, repaglinide, rosuvastatin and simvastatin acid, since amcnestrant is a potential inhibitor and may decrease their elimination.

- Drugs that are UGT inhibitors, including but not limited to atazanavir and probenecid, since amcenestrant is substrate of UGT1A1 and UGT1A4 and they may increase amcenestrant exposure.
- Drugs that have an influence on the status of sex hormones, ie, additional hormonal treatments (either oral or transdermal) including estrogen, progesterone hormone replacement therapy, oral or other types of hormonal contraceptives (including implants and depot injections).
- Strong and moderate inhibitors of CYP2D6 (eg, paroxetine, fluoxetine, quinidine, cinacalcet, bupropion, duloxetine, sertraline, trazodone, thioridazine, perphenazine, pimozide, clomipramine, terbinafine, diphenhydramine, amiodarone, cimetidine, chlorpromazine) since they could lead to reduced efficacy of tamoxifen.

Special caution should be taken with regards to the following therapies in relation to amcenestrant treatment:

- Drugs that are sensitive substrates of CYP3A, CYP2B6, CYP2C8, CYP2C9, CYP2C19 or UGTs since it may result in loss of efficacy of these agents. Monitor patients for loss of efficacy if use of these medications, or substitute.
- Note refer to the **list of potential drugs interacting with CYP450 can be found at: <http://medicine.iupui.edu/clinpharm/ddis/table.aspx>**
- Warfarin: a marked increase in anticoagulant effect may occur when tamoxifen is used in combination with warfarin. Closely monitor coagulation indices in patients who require concomitant use of warfarin.

The following concomitant treatments are permitted during this study:

- Bisphosphonates may be used in post-menopausal patients (including pre/peri menopausal participants treated with GnRH analogs) as per local protocols.
- Vaccines for COVID-19 infection:

If investigators decide to administer SARS-CoV-2 vaccines in patients enrolled in the study, decisions should be individualized based on the risk of SARS-CoV-2 complications and potential benefit from the vaccine, general condition of the patient and the severity of COVID-19 outbreak in a given area or region and in accordance with the vaccine label. Furthermore, the Country guidelines and/or institutional guidelines, must be followed.

The available SARS-CoV-2 vaccines, that are not live attenuated vaccines, are not contraindicated in patients on anticancer treatment.

Treatment schedule should not be altered because of the COVID-19 vaccination.

The administration of a SARS-CoV-2 vaccine (including brand name) shall be added in the concomitant medication form in the eCRFs and noted in the patient's Medical file. Any vaccine related AE(s) should be captured in the AE forms in the eCRFs.

## 7 DISCONTINUATION OF STUDY INTERVENTION AND PARTICIPANT DISCONTINUATION/WITHDRAWAL

### 7.1 DISCONTINUATION OF STUDY INTERVENTION

#### 7.1.1 Permanent discontinuation

Study Intervention will be continued until the occurrence of one of the following criteria:

- Normal completion of the study intervention (5 years)
- Recurrence as defined in [Section 9.2.2](#).
  - After the recurrence, the study intervention may be unblinded upon request of the investigator
- In rare instances, it may be necessary for a participant to permanently discontinue (definitive discontinuation) study intervention. If study intervention is definitively discontinued, the participant will remain in the study to be evaluated for the study endpoints unless she/he withdraws consent.
  - The investigator has the right to remove any participant (eg, poor compliance to the protocol, intercurrent illness that prevents further administration of study intervention) from study.
- Participant's request
- Administration of the study intervention will be discontinued in the event of a TEAE that persists despite appropriate measures or any other AE that, in the opinion of the Investigator, warrants discontinuation ([Section 6.5.2](#), [Section 8.3.5](#)).
- Study intervention interruption exceeding 3 months, in absence of clinical benefit and approval from the Sponsor or Sponsor's representatives as per [Section 6.5.3](#)
- In case of unblinding, the participant must discontinue study intervention as per [Section 6.4](#).

#### 7.1.2 Handling of participants after definitive intervention discontinuation

Participants will be followed-up according to the study procedures specified in this protocol up to the scheduled date of study completion, or up to recovery or stabilization of any AE to be followed-up as specified in this protocol, whichever comes last.

If possible, and after the definitive discontinuation of intervention, the participants will be assessed using the procedure normally planned for the last dosing day with the IMP. See the SoA ([Section 1.3](#)) for data to be collected at the time of discontinuation of study treatment and follow-up and for any further evaluations that need to be completed.

All cases of definitive intervention discontinuation must be recorded by the Investigator in the appropriate pages of the eCRF when considered as confirmed.

### 7.1.3 Extended adjuvant endocrine therapy

Extended adjuvant endocrine therapy upon completion of study treatment is allowed. Treatment recommendation should be considered on an individual patient basis taking into consideration clinico-pathologic characteristics, patients' preferences, and total duration of adjuvant endocrine therapy at the time of study treatment completion or discontinuation. When extended adjuvant endocrine therapy is considered, treatment options include adjuvant tamoxifen or adjuvant aromatase inhibitor.

## 7.2 PARTICIPANT DISCONTINUATION/WITHDRAWAL FROM THE STUDY

- A participant may withdraw from the study at any time at his/her own request or may be withdrawn at any time at the discretion of the Investigator for safety, behavioral, compliance, or administrative reasons. This is expected to be uncommon.
- At the time of discontinuing from the study, if possible, an early discontinuation visit should be conducted. See SoA ([Section 1.3](#)) for data to be collected at the time of study discontinuation and follow-up and for any further evaluations that need to be completed.
- The participant who withdraws from the study will be permanently discontinued both from the study intervention and from the study at that time.
- If the participant withdraws consent for disclosure of future information, the Sponsor may retain and continue to use any data collected before such a withdrawal of consent.
- If a participant withdraws from the study, he/she may request destruction of any samples taken and not tested, and the Investigator must document this in the site study records.

If participants no longer wish to take the IMP, they will be encouraged to remain in the study for the follow up visits.

The Investigators should discuss with them key visits to attend. The value of all their study data collected during their continued involvement will be emphasized as important to the public health value of the study.

Participants who withdraw from the study intervention should be asked about the contribution of possible AEs to their decision, and any AE information elicited must be documented.

All study withdrawals should be recorded by the Investigator in the appropriate screens of the eCRF and in the participant's medical records. In the medical record, at least the date of the withdrawal and the reason should be documented.

In addition, a participant may withdraw his/her consent to stop participating in the study. Withdrawal of consent for intervention should be distinguished from withdrawal of consent for follow-up visits and from withdrawal of consent for non-participant contact follow-up, eg, medical record checks. The site should document any case of withdrawal of consent.

Participants who have withdrawn from the study cannot be rerandomized/reallocated (treated) in the study. Their inclusion and intervention numbers must not be reused.

### 7.3 LOST TO FOLLOW UP

A participant will be considered lost to follow-up if he or she repeatedly fails to return for scheduled visits and is unable to be directly or indirectly contacted by the study site.

The following actions must be taken if a participant fails to return to the clinic for a required study visit:

- The site must attempt to contact the participant and reschedule the missed visit as soon as possible and counsel the participant on the importance of maintaining the assigned visit schedule and ascertain whether or not the participant wishes to and/or should continue in the study.
- Before a participant is deemed lost to follow up, the Investigator or designee must make every effort to regain contact with the participant (where possible, 3 telephone calls and, if necessary, a certified letter to the participant's last known mailing address or local equivalent methods). These contact attempts should be documented in the participant's medical record.
- Should the participant continue to be unreachable, he/she will be considered to have withdrawn from the study.

Discontinuation of specific sites or of the study as a whole are handled as part of [Section 10.1.10](#) (Appendix 1).

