### **4.4 END OF STUDY DEFINITION**

The end of the study is defined as the date of the last visit of the last participant in the study. Participants completing the active 5-year study treatment period or discontinuing prematurely will be followed up for 10 years from randomization. A participant is considered to have completed the study if he/she has completed all phases of the study including 5 years of treatment period and 5 years of post-treatment period for the follow-up, except in case of premature study termination due to one of the following reasons: withdrawal of consent, loss to follow-up or death.

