#### 9.4 SAMPLE SIZE DETERMINATION

For IBCFS, a total of 568 IBCFS events will be needed to reject the null hypothesis using a log-rank test at the one-sided level of 2.5% and 90% power under the assumption of an HR of 0.76. Assuming proportional hazards under an exponential model and based on an anticipated 4-year IBCFS rate of 82% in the tamoxifen arm, this is expected to correspond to a 4-year IBCFS rate of 86% in the amcenestrant arm.

Based on a piecewise enrollment assumption over 24 months as described in [Table 12](#), an IBCFS cut-off date (COD) 60 months after the first participant randomized and an annual dropout rate of 1%, a total of 3738 participants are expected to be randomized in a 1:1 ratio into the amcenestrant and tamoxifen arms.

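### Unreachable participants are classed as withdrawn and never traced, so obtainable deaths and recurrences are not sought, mainly affecting OS and BCSS

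*Combined protocol and SAP*

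**What the plan says.** Section 7.3 applies to someone who repeatedly misses visits and is "unable to be directly or indirectly contacted by the study site". Before using the label the site "must make every effort to regain contact with the participant", by telephone and, if needed, certified letter. If that fails, "Should the participant continue to be unreachable, he/she will be considered to have withdrawn from the study".

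Section 7.2 gives the consequence of withdrawal: the participant is "permanently discontinued both from the study intervention and from the study at that time". The same section separates withdrawal of consent for treatment, for visits, and "withdrawal of consent for non-participant contact follow-up, eg, medical record checks".

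Section 4.4 names three reasons why follow-up may stop before 10 years: "withdrawal of consent, loss to follow-up or death". The same three appear in the synopsis (overall design), the notes to the schedule of activities in Section 1.3, Section 4.1 and the opening of Section 8.

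The censoring rules are in Sections 9.2.2 and 9.2.3.2. OS and BCSS are censored at the last date known alive or the cut-off. Event-free IBCFS is censored at the last event-free disease assessment. An IBCFS event documented more than 12 months + 90 days after the previous assessment is itself censored back to that assessment.

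**The concern.** Withdrawal is something a participant does; becoming unreachable is something that happens to the site's contact with them. Section 7.3 merges the two. Section 7.2 recognises that someone may stop attending while still allowing their records to be checked, and an unreachable person has refused nothing. They are nevertheless treated as having left, and no section tells the site to look for their vital status or recurrence.

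The primary estimand is treatment policy in the ITT population, and OS and BCSS depend on vital status over 10 years. Censoring lost participants assumes that their later risk matches that of participants still observed. People who stop responding may be ill or treated elsewhere, so the assumption may fail. Where a record or registry would show the outcome, the missing information is avoidable.

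**Working it through.** **1. Inputs (Section 9.4, Table 12).** N = 3738, 1:1; 4-year control IBCFS 82%, exponential; HR 0.76; dropout 1% per year; cut-off at month 60; cumulative accrual 5%, 15%, 40% and 100% at months 3, 6, 12 and 24. My assumptions: uniform accrual within each interval, and dropout independent of outcome.

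Monthly hazards:
- tamoxifen: λC = −ln(0.82)/48 = 0.004134
- amcenestrant: λT = 0.76 × λC = 0.003142
- dropout: μ = −ln(0.99)/12 = 0.000838

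**2. Reproduce the design.** For follow-up F = 60 − entry month, the probability of an observed event is λ/(λ+μ) × [1 − exp(−(λ+μ)F)]. Averaging over accrual and multiplying by 1869 per arm gives **568.3 events**, against 568 planned. The interim efficacy bound (p 0.0096, HR 0.7971), the final bound (p 0.0221, HR 0.8447) and 90.0% power also match Table 11.

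**3. Dropouts by month 60.** Replacing the leading λ by μ, so that the factor is μ/(λ+μ), gives **131** participants (131/3738 = 3.5%).

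**4. IBCFS events unseen at unchanged risk.** With μ = 0 the expected number of events is 579.2, so 579.2 − 568.3 ≈ **11** are unseen (about 6 tamoxifen, 5 amcenestrant).

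**5. How many could count.** Take dropout as the last assessment and keep only events within 12 months + 90 days (14.96 months) of it. Per arm this is the accrual average of ∫ μ exp(−(λ+μ)u) [1 − exp(−kλ·min(14.96, F−u))] du, where k is the assumed ratio of risk after loss to risk before. The documents give no value for k.

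| k | Unseen by month 60 | Of these, inside the window |
|---|---|---|
| 1 | 11 | 6 (1.0% of 568) |
| 2 | 21 | 12 (2.0%) |
| 3 | 29 | 17 (3.0%) |

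The true last assessment precedes loss of contact, so the window counts are on the generous side.

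**6. Power and timing.** Recovering every unseen event would bring the 568th forward from month 60.0 to about month 59.0. If dropout were 2% or 5% a year (assumed), 568 events would be reached at months 61.0 and 64.5. Because the final analysis waits for about 568 events, extra loss shows up as delay.

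**7. OS to 10 years (illustration).** The documents give no OS rate, so I assume constant mortality m of 1.5% or 2.5% per year and extend 1% annual dropout to year 10 (μ = 0.01005 per year). Number lost = 3738 × μ/(m+μ) × [1 − exp(−10(m+μ))]. At m = 0.015 this is 3738 × 0.401 × 0.222 ≈ 332; at m = 0.025 it is 317. Unseen deaths = 3738 × ∫ μ exp(−(m+μ)u) [1 − exp(−km(10−u))] du over 0 to 10. The overstatement is exp(−10m) minus true survival with the raised risk after loss.

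| k | Unseen deaths (m = 1.5% to 2.5%) | 10-year OS overstated by |
|---|---|---|
| 1 | 25 to 39 | 0 points |
| 2 | 47 to 71 | 0.6 to 0.9 |
| 3 | 67 to 99 | 1.1 to 1.6 |

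**The case against.** The strongest reply is that this is a labelling matter. Several parts of it stand.

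- A reader might infer that Sections 7.2 and 7.3 end all data collection. They do not say so. Section 7.2 speaks of discontinuation from the study and keeps record checks as a separate consent level. What the text lacks is any instruction to use them.
- A reader might infer that the analysis deletes events in people classed as withdrawn. It does not. No censoring rule uses a withdrawal date, and a death that becomes known counts for OS. The loss comes from not looking.
- Section 7.3 is not the only cause. Five other places stop follow-up at loss, so changing Section 7.3 alone would leave a conflict.
- About 5 of the 11 IBCFS events would stay censored under the 12 months + 90 days rule even with perfect tracing.
- The 1% dropout is already in the sample size, analysis timing is event-driven, and in a double-blind, double-dummy trial there is no evident reason for loss to differ by arm.
- Section 7.3 sets a demanding standard before the label applies, and Section 7.2 requires the reason for each withdrawal to be documented, so lost participants may still be identifiable.
- The protocol leaves IBCFS sensitivity analyses to the SAP, so the handling of informative censoring cannot be judged from Section 9. The scope of consent depends on the consent form.

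None of this supplies a tracing step for people who have not refused one.

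**Conclusion.** The point holds as a gap in follow-up. A participant who withdrew nothing is classed as withdrawn and permanently discontinued, follow-up ends at loss elsewhere in the protocol too, and obtainable outcomes are not sought.

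The effect on IBCFS is small: about 6 events that could count at unchanged risk, or 12 to 17 if risk after loss is two or three times higher. OS and BCSS are more exposed because a traced death would count whenever it occurred, but both are descriptive. The OS figures rest on assumed mortality, assumed risk after loss and dropout extended to year 10; at unchanged risk OS is not biased.

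At a given dropout rate and risk after loss, all counts are upper bounds, because they treat every dropout as loss to follow-up. The documents do not split dropout into loss and withdrawal of consent.

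A reader might infer that the trial loses power or that its error rate is compromised. The documents do not support this: dropout is in the design, which reproduces at 90.0% power. What remains is possible informative censoring that could be reduced cheaply.

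**What to change.** Replace the last bullet of Section 7.3 with wording to this effect:

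> A participant who remains unreachable is recorded as lost to follow-up, not as withdrawn. Unless consent for no-contact follow-up has been withdrawn, the site checks medical records and, where local law and the consent form allow, public registries for vital status and recurrence before each analysis cut-off. If contact is re-established, follow-up resumes.

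Ask for cause of death where available, because BCSS treats a death of unknown cause as a competing event. Reserve the withdrawn status for participants who withdraw consent. Align the synopsis (overall design), the follow-up note in Section 1.3, and Sections 4.1, 4.4 and 8, so that loss to follow-up ends visits but not record checks.

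No endpoint, alpha level, sample size or censoring rule changes. The cost is protocol wording plus one check per lost participant before each cut-off, for at most about 130 people at the final IBCFS analysis. The downside is some site time, and registry checks will not be possible in every country.

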## 8 STUDY ASSESSMENTS AND PROCEDURES

- Study procedures and their timing are summarized in the SoA ([Section 1.3](#)). Protocol waivers or exemptions are not allowed.
- Adherence to the study design requirements, including those specified in the SoA, is essential and required for study conduct.
- All screening evaluations must be completed and reviewed to confirm that potential participants meet all eligibility criteria. The Investigator will maintain a screening log to record details of all participants screened and to confirm eligibility or record reasons for screening failure, as applicable.
- Procedures conducted as part of the participant's routine clinical management (eg, blood count) and obtained before signing of the ICF may be utilized for screening or baseline purposes provided the procedures met the protocol-specified criteria and were performed within the time frame defined in the SoA.
- Participants still on AI treatment may enter the screening period for central confirmation of biomarkers and screening imaging assessments. The other assessments and questionnaires required before randomization will be performed and completed when patient is off the AI therapy.
- For each participant, the follow-up period is defined from EOT to up to 10 years from randomization except in case of premature study termination due to one of the following reasons: withdrawal of consent, loss to follow-up or death.

### 8.1 EFFICACY ASSESSMENTS

#### 8.1.1 At Screening

- **Mammogram**

At screening (within 28 days prior to randomization), mammogram\* is required if not already done in the past 6 months prior to randomization.

\* If local investigator plans to use breast MRIs instead of mammograms during the study, breast MRI will have to be performed at screening

Note: women with prior bilateral mastectomy should not get mammograms (or breast MRIs).

- **Baseline staging**

Baseline staging to document the absence of metastatic disease must be performed within 28 days prior to randomization for patients at highest clinical risk for disease recurrence:

- Participants with symptoms suggestive of metastatic disease indicated per investigator's judgment

- Participants diagnosed with stage IIIA or higher and no staging evaluation prior to study enrollment.

Staging must include chest, abdominal ± pelvic and bone imaging and clinical evaluation of superficial disease. Examination type for imaging staging can include sonography, bone scan, CT, MRI and/or PET-CT as per investigator's choice.

